## 7. ADVERSE EVENTS AND ADVERSE EVENT REPORTING

At each study visit, patients will be evaluated for new AEs and the status of existing AEs. The Investigator may elicit symptoms using an open-ended question, followed by appropriate questions that clarify the patient's verbatim description of AEs or change in concomitant medications. The enrolling Investigator is responsible for safety oversight of data for all visits unless the patient is transferred to another site for all subsequent visits. All AEs from the time of signing the informed consent through follow-up will be recorded on the eCRF.

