#### 7.1.2. Adverse Events Occurring After Study Treatment

All AEs that occur from the time of the administration of the first dose of investigational product through the end of the safety follow-up will be considered treatment-emergent AEs (TEAEs).

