2. STUDY DESIGN

2.1. Synopsis of Study Design

This is a randomized, double-blind, placebo-controlled, Phase 3, multisite study of edasalonexent in pediatric patients with DMD.

[figure not shown]
Eligible patients will be ambulatory boys aged ≥ 4.0 to < 8.0 years with a confirmed diagnosis of DMD who have not use steroids within 24 weeks prior to treatment start (Day 1). In regions where eteplirsen is approved or there is an established access program, patients who have received at least 24 weeks of treatment with eteplirsen prior to Day 1 will be eligible.

As shown in [Figure 1](#), following a 4-week screening period to determine eligibility, approximately 126 patients will be randomized 2:1 to receive edasalonexent 100 mg/kg/day or placebo in a double-blind fashion daily for 52 weeks. Randomization will be stratified by baseline age (≤ 6.0 vs. > 6.0 years), baseline time to stand from supine (≤ 5 vs. > 5 seconds), treatment with eteplirsen (yes vs. no), and region (North America vs. Europe/Asia/Australia). Note that if siblings are enrolled, they will be assigned to the same treatment group.

Randomized patients (and enrolled siblings who are not randomized) will complete Baseline procedures and begin receiving study drug (edasalonexent or placebo) on Day 1. During the treatment period, patients will have site visits approximately every 13 weeks with site calls in between as specified in the Schedule of Assessments ([Table 1](#)). For those patients who do not enter the extension study, a safety follow-up should occur within 2 weeks of the last dose of study drug for collection of adverse events (AEs).

The length of a patient's participation in the study will be from the time of informed consent through the Week 52 visit. A patient will be considered to have completed the study when they have completed the Week 52 assessments. Patients who do not participate in the open-label extension study will be considered to have completed the study after they complete the safety follow-up.

Figure 1 Overview of Study Design

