2.4. Study Procedures

The schedule of assessments, as outlined in the study protocol, is provided in [Table 1](#).

Table 1: Schedule of Assessments

	Screen ^a	BL ^b	Double Blind, Placebo-Controlled Treatment (Weeks 1 - 52)									Safety F/U ^c
Study Week(s)	-4 - 0	0	3	6	13	19	26	32	39	45	52/ET ^d	
Informed Consent/Assent	X											
Site Visit ^e	X	X			X		X		X		X	
Site Call ^{e,f}			X	X		X		X		X		X
Med History/Demographics	X											
Confirm Eligibility	X	X										
Randomization ^g		X										
Vital Signs	X	X			X		X		X		X	
Weight	X	X			X		X		X		X	
Height		X					X				X	
Physical Examination	X	X			X		X		X		X	
AEs/Con Meds/Change in Function ^h	X	Continuous										
12-Lead ECG ⁱ	X						X				X	
Cardiac Monitoring ^j		X					X				X	
Hematology/Chemistry ^k	X	X			X		X		X		X	
ACTH/Cortisol ^k		X			X		X		X		X	
Urinalysis	X						X				X	
DNA Sample ^l		X										
Biomarkers, Gene Expression ^k		X			X		X		X		X	
NSAA, Stand from Supine, 10MWT, 4-Stair Climb, Muscle Strength, PUL ^l	X	X			X		X		X		X	
Videotape Functional Assessments ^m	X	X									X	
PODCI ⁿ		X									X	
Lateral Spinal Radiography, DXA ^o		X									X	
Nutritional Guidance ^p		X										
Drug Dispensation		X			X		X		X			
Drug Accountability			X		X		X		X		X	
Plasma PK ^q		X			X		X				X	

a Per Investigator's discretion, informed consent, medical history/demographic data and lab assessments may be completed remotely by a qualified medical professional.

- b The first day of study drug is “Day 1”; unless otherwise specified, all assessments should be completed within a 4 week window prior to Day 1.
- c Safety follow-up should occur within 2 weeks after the last dose of study drug. Patients continuing into the open-label extension study are not required to perform the safety follow-up.
- d If patient discontinues treatment early, patient will be asked to return for early termination (ET) visit prior to their last dose of study drug. Functional assessments performed within 6 weeks of discontinuing treatment do not need to be repeated at the ET visit. If the ET visit occurs after drug has been discontinued, certain assessments may be omitted per Sponsor discretion.
- e Weeks 6-19 should be conducted within the study week with a ± 4 -day window. Weeks 26-54 have a ± 10 -day window.
- f Per Investigator discretion, site calls may occur by telephone or use of other technology.
- g Randomization occurs after Screening assessments have been completed and eligibility is confirmed.

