4.13.1. Adverse Events

Adverse events will be coded using the MedDRA dictionary and displayed in tables and listings using System/Organ/Class (SOC) and Preferred Term (PT).

Analyses of adverse events will be performed for those events that are considered TEAEs, where treatment emergent is defined as any adverse event with onset after the administration of study medication through the end of the study (Week 52 visit) or any event that was present at Baseline but worsened in intensity or was subsequently considered drug-related by the investigator through the end of the study.

If the start date of an AE is partially or completely missing, then the date will be compared as far as possible with the date of the randomization. The AE will be assumed to be treatment emergent if it cannot be definitively shown that the AE did not occur or worsen during the post-randomization period (worst case approach).

The following general rules will be used:

- If the start day is missing, but the start month and year are complete, an AE will only be excluded as being on-study if the start month/year is before the month/year of randomization or if the stop date is before randomization.
- If the start day and month are missing, but the start year is complete, an AE will only be excluded as being on-study if start year is before the year of randomization or if the stop date is before randomization.
- If the start date is completely missing, an AE will be considered on-study unless the stop date is before randomization.

TEAE summaries will include the number and percentage of patients in each treatment group and overall. Summaries will include patients with:

- Any TEAEs
- Treatment-related TEAEs (Related, Possibly related)
- Maximum Severity of TEAEs
- Serious TEAEs, including any events resulting in death
- Treatment-related serious TEAEs
- TEAEs (and treatment-related TEAEs) leading to discontinuation of study drug

TEAEs are summarized by patient incidence rates, therefore, in any tabulation, a patient contributes only once to the count for a given adverse event (SOC or preferred term). TEAEs will also be summarized by SOC, PT, and severity and by SOC, PT, and relatedness. The most severe occurrence of a TEAE, as well as the most extreme relationship of the TEAE to the study procedure or treatment, will be used in tabulations of severity and relatedness in cases of multiple occurrences of the same TEAE.

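### The SAP closes the treatment-emergent AE window at the Week 52 visit, the protocol closes it at the end of the safety follow-up, and the difference is neither declared nor consistent with the SAP's own completion rule

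*SAP*

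**What the plan says.** Protocol 7.1.2 starts the window at the first dose and runs it "through the end of the safety follow-up will be considered treatment-emergent AEs (TEAEs". Protocol Section 7 sets collection to match: "All AEs from the time of signing the informed consent through follow-up will be recorded on the eCRF".

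SAP 4.13.1 restricts the AE tables: "Analyses of adverse events will be performed for those events that are considered TEAEs". It then defines such an event by "onset after the administration of study medication through the end of the study (Week 52 visit". A second limb adds events already present at Baseline that worsen, or are later judged drug-related, up to the end of the study. For incomplete start dates, the SAP compares the available date only with randomization and treats the event as treatment-emergent unless it clearly came before that.

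SAP 2.1 has two completion rules. The general one is "A patient will be considered to have completed the study when they have completed the Week 52 assessments". The other is "Patients who do not participate in the open-label extension study will be considered to have completed the study after they complete the safety follow-up". The same section gives the purpose of the last contact for boys outside the extension: "a safety follow-up should occur within 2 weeks of the last dose of study drug for collection of adverse events (AEs". Footnote c to SAP Table 1 exempts the others: "Patients continuing into the open-label extension study are not required to perform the safety follow-up".

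SAP Section 6 lists two departures from the protocol, the MMRM terms and the rank sum endpoint. Neither it nor the version history in SAP 1.2 mentions the AE window.

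**The concern.** The two documents use one term, treatment-emergent, with two end points, and the SAP is the document that will be programmed. Safety and tolerability are a secondary objective, and Protocol 9.12 puts TEAE and SAE incidence at the head of the safety assessment. If the parenthesis in SAP 4.13.1 is followed, the any-TEAE, related, severity and serious summaries omit events that the protocol counts. Those events come from a contact held in order to collect AEs. A reader comparing the report with the protocol would find tables that do not follow the stated definition, with nothing in the SAP to explain why.

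The partial-date rules make this uneven. They have a lower limit but no upper one, so a follow-up event with a complete date is left out while a poorly dated one can be kept.

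**Working it through.** **Reproducing the plan's own figure.** The protocol synopsis gives about 58 weeks of participation: 4 (screening) + 52 (dosing) + 2 (follow-up) = 58. The two follow-up weeks therefore lie beyond the dosing period and inside the protocol's AE window.

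**The definitions side by side.**

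| Item | Protocol | SAP |
|---|---|---|
| End of TEAE window | End of safety follow-up (7.1.2) | Week 52 visit (4.13.1) |
| Study completion, boys not entering the extension | After safety follow-up (3.3.3.1) | After safety follow-up (2.1) |
| AE recording | Through follow-up (Section 7) | Follow-up held to collect AEs (2.1) |
| Upper limit for partly dated AEs | Not addressed | None (4.13.1) |
| Difference declared | – | No (Sections 1.2 and 6) |

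**Who is affected.**

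- Completers entering the extension: no safety follow-up is required, so no gap arises from it.
- Completers not entering it: they have the follow-up and are the affected group. The group includes boys for whom the extension is unavailable as well as those who decline, because Protocol 3.3 makes it subject to ethics and regulatory approval.
- Boys who withdraw from the study without a Week 52 visit: SAP 4.13.1 does not say where their window ends.
- Boys who stop treatment but stay in the study: Protocol 5.2.5 separates stopping treatment from withdrawal, and 7.1.3 keeps recording AEs until study completion. If they attend Week 52, the SAP wording already covers them to that visit.

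**Which events.** The second limb of the SAP definition covers only events present at Baseline, so it does not recover a new event found at follow-up. The summary of TEAEs leading to discontinuation should not be affected, because these boys have already completed treatment.

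**Size of the gap per boy.** Assume the Week 52 visit and the last dose both fall on Day 364, and follow-up takes place at the two-week limit.

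- SAP window: 52 × 7 = 364 days.
- Protocol window: 364 + 14 = 378 days.
- Gap: 378 − 364 = 14 days (Days 365 to 378), and 14 / 378 = 3.7% of the protocol window.

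The day numbers are nominal. SAP 5.2 schedules Week 52 at 364 days from randomization, which is Day 365 if randomization falls on Day 1, and the visit has a ±10-day window. These shift the dates but not the length. A last dose before the visit shortens the gap. A late follow-up call lengthens it, since the two weeks are worded as a recommendation.

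**Number of boys.** The documents give neither the share not entering the extension nor the AE rate in follow-up. For illustration only:

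- Completers: 126 × (1 − 0.20) ≈ 101, using the plan's dropout assumption.
- Low end, with 5% not entering and a 5% chance of a new AE: 101 × 0.05 × 0.05 ≈ 0.3 boys.
- High end, with 50% not entering and a 20% chance: 101 × 0.50 × 0.20 ≈ 10 boys.

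The 5% to 50% and 5% to 20% ranges are assumptions, so 0.3 to 10 shows an order of magnitude and is not an estimate.

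**The case against.** The strongest reply is that SAP 4.13.1 speaks of the end of the study, and SAP 2.1 places that after the safety follow-up for the boys in question. The Baseline-event limb also refers to the end of the study without a Week 52 parenthesis. On that reading the two documents agree. This stands in part: the SAP is internally inconsistent and does not make a clean choice of cut. But the parenthesis names a visit explicitly, and a programmer would reasonably follow it.

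A second reply is that Section 6 covers changes to planned analyses, while the protocol's window sits in its AE-reporting section and Protocol 9.12.3 gives no window. That is a fair reason to call this a mismatch of definitions rather than a concealed change of analysis. It still needs declaring or removing, because the definition decides what enters the planned tables.

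A third reply is that little is lost. Safety comparisons are qualitative (SAP 4.13), eCRF data are listed (Protocol 9.1), and deaths and SAEs have their own by-patient listings (SAP 4.13.1). All of this stands and limits the weight of the point. Listings do not replace incidence tables, however.

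A reader might also infer three stronger things. The first is that follow-up AEs are not collected or disappear from the report; they are recorded and listed. The second is that the cut favours one arm; nothing in the documents shows a direction. The third is that every boy who stops drug early should have his window closed at a follow-up timed from his last dose. The documents do not support this, because Protocol 7.1.3 keeps recording AEs in boys who remain in the study, and such a rule could remove events that the SAP now counts.

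**Conclusion.** The mismatch is certain on the text, and its consequence is modest. Under the SAP as written, new, fully dated AEs starting after the Week 52 visit in completers who do not enter the extension are TEAEs by the protocol but fall outside the SAP's TEAE summaries. The loss is nominally up to about 14 days of observation per affected completer. That rests on a last dose on the day of the Week 52 visit and an on-time follow-up. The number of events is unknown. The effect is confined to descriptive safety tables and touches no efficacy result. The point should be corrected before the tables are programmed, but it does not threaten the trial's conclusions.

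**What to change.** In SAP 4.13.1, replace the Week 52 end point with ends stated by group:

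- completers not entering the extension: the end of the safety follow-up;
- patients entering the extension: the Week 52 visit;
- patients who withdraw from the study: their safety follow-up or last study contact;
- patients who stop treatment but stay in the study: study completion, in line with Protocol 7.1.3, so that no event now counted is dropped.

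Keep the limb for events present at Baseline and apply the same ends to it. Give the partial-date rules the same upper limit, so that complete and incomplete dates are judged against one window.

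If the Week 52 cut is deliberate, declare it in SAP Section 6 as a difference from Protocol 7.1.2 and tabulate follow-up AEs separately.

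The cost is SAP wording and a date cut in the AE dataset. No new data are needed, because AEs are already recorded through follow-up.

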### 7.1. Timeframe for Collection of Adverse Events

#### 7.1.1. Adverse Events Occurring Prior to Study Treatment

All AEs that occur between the time informed consent is provided and the patient's receipt of the first dose of investigational product will be considered pretreatment AEs.

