4.9. Treatment Exposure and Compliance

Throughout the study, patients and their parents/caregivers will complete a diary documenting study drug administration and diet compliance. For the Safety Population, treatment duration, number of administrations, and compliance (summarized by assessing capsule count) will be summarized by treatment group and overall.

Treatment Duration: Treatment Duration will be the number of days from the patient's first dose until their Week 52 visit. If the patient discontinued from the study and did not have a Week 52 visit the subject's Early Termination visit will be used (note: if the subject does not have an early termination visit, the last visit will be used).

The patient's date of first dose is determined by the study drug administration at baseline:

- If for the baseline visit the "first dose of the day administered in clinic" = "No" (i.e., variable EX.EXPERF= "N") then the date of first dose is the date in the field EX.EXSTDAT (i.e., the "Date of study drug administration").
- Otherwise the date of first dose is the date of the baseline visit.

Expected Average Daily Dose: The expected number of capsules that a patient is to take each day is specified at each visit that the patient receives new study medication (e.g., Baseline, Week 13, Week 26, and Week 39, but there may be distribution at unscheduled visits as well). The daily total of capsules is broken up into morning/afternoon/evening administration. The exact capsule count per dose and the capsule dose strength (i.e., 250 mg or 100 mg) will be provided through the IXRS based on the patient weight at each study visit.

The periods are:

- 1st day patient takes study medication to the day before the Week 13 visit
- Week 13 to the day before the Week 26 visit
- Week 26 to the day before the Week 39 visit

- Week 39 to the day of the Week 52 visit.

Please note the following potential modifications to these periods:

- If the patient discontinues the study early, the corresponding period will end at the date of the early termination visit.
- If the patient has an unscheduled visit where study drug is dispensed the periods will be updated to account for this visit. The following is an example of the update to the algorithm where the patient had an unscheduled visit between the Week 26 and Week 39 visits.
 - 1st day patient takes study medication to the day before the Week 13 visit
 - Week 13 to the day before the Week 26 visit

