4.13.8. Prior and Concomitant Medications and Therapeutic Procedures

Prior and concomitant medications and therapeutic procedures will be coded using the WHO Drug dictionary. Results will be tabulated by Anatomic Therapeutic Class (ATC; level 4) and preferred term.

Prior medications are those that started and stopped before exposure to study medication (i.e., date of first dose); concomitant medications are all medications taken during the study period, including those started before but on going at first dose. Where a medication start date is partially or fully missing, and it is unclear as to whether the medication is prior or concomitant, it will be assumed that it is concomitant.

The use of concomitant medications will be included in a by-patient data listing and summarized in a table. The use of prior medications and therapeutic procedures will be included in by-patient data listing.

Additionally, a by-patient listing of concomitant medications that started or stopped during the treatment period will be created, specifically indicating the following:

- Treatment Group
- Patient ID:
- Medication Name/Preferred Term/ATC Term Modification:
- Indication

- Start/Stop Date (ongoing)
- Dose (unit)
- Frequency/Route

The determination of a medication starting or stopping with the treatment period will be based on the following:

- Date of First Exposure to Treatment \leq Date of medication start date \leq Date of Last Exposure to Treatment

(i.e., $ADCM.TRTSDT \leq ADCM.ASTDT \leq ADCM.TRTEDT$)

The following general rules will be used for partially missing medication start dates:

- If the start day is missing, but the start month and year are complete, the medication will be considered as having started during the treatment period if the month/year is between the treatment start/stop month/year values (inclusive).
- If the start day and month are missing, but the start year is complete, the medication will be considered as having started during the treatment period if the year is between the treatment start/stop year values (inclusive).
- If the start date is completely missing, the medication will not be considered as having started in the treatment period.

- Date of First Exposure to Treatment \leq Date of medication stop date \leq Date of Last Exposure to Treatment

(i.e., $ADCM.TRTSDT \leq ADCM.AENDT \leq ADCM.TRTEDT$)

The following general rules will be used for partially missing medication stop dates:

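### Partial-date rules for adverse events compare with randomisation although TEAEs are defined from first dose, so an event that ended before any drug can be counted as treatment-emergent (low priority)

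*SAP*

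**What the plan says.** The definitions start at drug. SAP 4.13.1 states that "treatment emergent is defined as any adverse event with onset after the administration of study medication", and adds events present at Baseline that worsened or were later judged drug-related. Protocol 7.1.2 counts TEAEs "from the time of the administration of the first dose of investigational product through the end of the safety follow-up". Protocol 7.1.1 covers the time from consent onwards: AEs up to the patient's "receipt of the first dose of investigational product will be considered pretreatment AEs".

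The rules for incomplete start dates, also in SAP 4.13.1, use a different date. The lead sentence says "then the date will be compared as far as possible with the date of the randomization". The default is that an AE is treatment-emergent if it "cannot be definitively shown that the AE did not occur or worsen during the post-randomization period (worst case approach"). With the start day missing, an AE is excluded only if the "start month/year is before the month/year of randomization or if the stop date is before randomization". The bullets for a missing day and month, and for a completely missing date, also use randomisation.

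On how the two dates relate, Protocol 6.2 places randomisation at Baseline. SAP 4.9 takes the baseline visit date as the date of first dose, with one exception: if the first dose of the day was not given in clinic, "then the date of first dose is the date in the field EX.EXSTDAT". For medications, SAP 4.13.8 uses first dose: "Prior medications are those that started and stopped before exposure to study medication (i.e., date of first dose").

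**The concern.** One classification has two reference dates within one section. An AE with a complete start date is judged against first dose, and an AE with an incomplete one against randomisation. Where the dates differ, the interval between them is pretreatment under the protocol but counts as on-study under the SAP's partial-date rules. An event that ran its whole course in that interval then enters the TEAE tables only because part of its start date is missing.

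SAP section 6 lists the changes from the protocol's planned analyses, and a new reference date for TEAEs is not among them. Nothing shows that the difference was intended. At stake is the agreement of the TEAE tables with their own definition, not an efficacy conclusion or a formal test.

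**Working it through.** The plan gives no figure to reproduce. The check is to apply the three bullets twice, with randomisation and then with first dose as the reference date, to events whose true position is known. The documents do not report gaps between the two dates, so the dates below are assumed.

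**Rule.** With reference date R, exclude the AE if its stop date is before R, or if its recorded start month/year (or start year alone) is before that of R. Otherwise count it as a TEAE.

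**Assumed case A:** randomised 30 Jan 2019, first dose 2 Feb 2019, a gap of 3 days.

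| Recorded AE dates | R = randomisation (as written) | R = first dose |
|---|---|---|
| 1. Start Jan 2019, day missing; stop 31 Jan 2019 | TEAE | not TEAE |
| 2. Start completely missing; stop 1 Feb 2019 | TEAE | not TEAE |
| 3. Start 2019, day and month missing; stop 31 Jan 2019 | TEAE | not TEAE |
| 4. Start Jan 2019, day missing; ongoing | TEAE | not TEAE by onset |

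**Assumed case B:** randomised 31 Dec 2019, first dose 2 Jan 2020.

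| Recorded AE dates | R = randomisation (as written) | R = first dose |
|---|---|---|
| 5. Start 2019, day and month missing; ongoing | TEAE | not TEAE by onset |

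**Reading the results**

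- Events 1 to 3 stopped before first dose. They cannot have begun or worsened on drug, so they are errors under the SAP's own definition.
- Events 4 and 5 began before first dose but were still present when dosing started. They fail the onset part of the definition. They may still qualify if they worsened or were later considered drug-related. The rules as written keep them without asking.

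**Size per patient.** For a gap of g days and a completely missing start date, the stop dates wrongly kept run from the randomisation date to the day before first dose, which is exactly g dates. In case A these are 30 Jan, 31 Jan and 1 Feb, so g = 3. At g = 0 there are none, and the two versions agree on every test event in case A when both dates are set to 30 Jan 2019.

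**When the start month matters.** Events like 4 also need the gap to cross a month end. Over a 365-day year with 12 month ends, the share of randomisation dates for which this happens is 12g/365 for short gaps:

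- g = 1: 12/365 = 3%
- g = 3: 36/365 = 10%
- g = 7: 84/365 = 23%

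These are shares of possible randomisation dates under assumed gaps. They are not shares of boys with a misclassified event, which would also require an AE with an incomplete start date in the relevant month.

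**The case against.** The strongest defence is that the situation should be rare. Randomisation and drug dispensing both belong to the Baseline visit, and SAP 4.9 takes that visit's date as first dose by default. Even a first dose taken at home may fall on the same calendar day. Protocol 7.4 asks for date and time of onset and resolution, and Protocol 10.3.2 says that incomplete entries will be queried. This stands, and it limits the size. It does not remove the inconsistency, because SAP 4.9 has a separate branch for a first dose with its own date.

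A second defence is that the SAP takes a worst-case approach deliberately. That covers events whose timing cannot be established. It does not cover an event whose stop date shows that it ended before drug.

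Three stronger readings are tempting, but the documents do not support them:

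- **Gaps of up to 28 days.** A reader might take these from footnote b of Protocol Appendix 1, which allows assessments in the 4 weeks before Day 1, and conclude that about 92% of boys are exposed (12 × 28/365). The footnote is a window for assessments and does not describe randomisation four weeks before dosing. The 92% is again only a share of randomisation dates.
- **Every event that began before first dose is certainly misclassified.** This fails for ongoing events, which can be valid TEAEs through worsening or a later judgement of relatedness.
- **Treatment-related and serious TEAE counts are inflated.** This is not shown. An event that ended before any drug is unlikely to be rated related, and SAEs must be reported within 24 hours, which makes a missing onset date less likely.

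**Conclusion.** Wrong as written, low priority. The partial-date rules in SAP 4.13.1 contradict the TEAE definition in the same section and in Protocol 7.1.1 and 7.1.2.

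- The clear error is confined to AEs with an incomplete start date and a stop date on or after randomisation but before first dose.
- AEs that began before first dose and were ongoing at it are kept by default. They should be judged on worsening or relatedness.

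Both need first dose to fall on a later calendar date than randomisation. How often that happened, and how many start dates are incomplete, is not given, so no count can be derived. Few events are expected. The same rule applies to both arms under blinding and errs towards over-counting. SAP 4.13 plans no inferential comparison of AEs, so the effect is limited to descriptive tables.

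**What to change.** In SAP 4.13.1, replace randomisation with first dose of study drug as the reference date in three places: the lead sentence, the phrase describing the post-randomisation period, and all three bullets. Use the date derived in SAP 4.9, which matches the reference already used in SAP 4.13.8.

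State that an AE whose recorded start month or year is before that of first dose, and which was ongoing at first dose, counts only under the worsened or drug-related part of the definition. Keep the worst-case default for AEs whose timing or worsening relative to first dose cannot be determined.

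The cost is a wording change in one section and one date variable in the AE program. No new data are needed, and no other planned analysis depends on keeping randomisation as the reference here.
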